## 4 STUDY SETTING

The study will be situated in Belgian family practice. We estimate that about 124 PCPs will be included in the study (300 physicians working in 124 different PCPs). The targeted professionals are active family physicians. The study will be conducted in practices collaborating with one of three private laboratories:

1. **MCH** (Medisch Centrum Huisartsen, [name], 3000 Leuven),
2. **Anacura** ([name], 9940 Evergem), or
3. **AML** (Algemeen Medisch Laboratorium, [name], 2020 Antwerpen).

These laboratories collaborate with physicians throughout Flanders, primarily located in the region of Leuven/Flemish Brabant (MCH), East- and West-Flanders (Anacura) and Antwerp and East-Flanders (AML). Both MCH and Anacura provide laboratory services to around 500 primary care physicians, whereas AML delivers services to about 1000 physicians. All laboratories cooperate primarily with primary care physicians, but in a much smaller amount also with some private specialist practices. The study will be conducted amongst family physicians prepared to change their laboratory testing ordering from paper-based to an online CPOE.

Currently around 30% of collaborating physicians use the laboratory CPOE to order laboratory tests (personal communication 2016). All other physicians use a paper-based order form to order tests. The paper-based order forms consist of a selection of common (and less common) laboratory test, often ordered by type, such as chemistry, microbiology, haematology, etc. Figure 2 illustrates a paper-based laboratory form. An important goal will be to be able to include physicians naïve to the use of CPOE. See 8.1 for our strategies to maximise recruitment of physicians.

The study by De Sutter et al (De Sutter 2007) showed that for a series of five key tests (ureum, total protein, amylase, thrombocytes, and chloride), inappropriateness was as high as 77.5 or even 100%. For these tests, the prevalences (measured as the number of test panels including one of these test over the total number of test panels) found in their study are similar to those found at the three collaborating laboratories (data from 2016). Table 2 summarizes these prevalences. On average physicians order 14.61 tests per panel at AML, 14.2 tests at Anacura and 14.25 tests at MCH (personal communication). In the study by De Sutter et al, the average amount of tests per panel was similar, at 13.3 tests (De Sutter 2007).

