### 9.3.3 Secondary outcome analysis

#### 9.3.3.1 Missed diagnoses

The proportion of patients with a missed diagnosis will be analysed by means of a logistic GEE model that includes a factor for allocated group and uses PCP as the clustering variable. An independent working correlation matrix will be used. The proportion of patients with a missed diagnosis and associated 95% confidence intervals will be estimated from the model.

The difference in proportions will be obtained by subtracting the two proportion. The associated standard error will be calculated from the rules for the variance of a difference between two independent estimates. The 95% confidence interval for the difference will be calculated.

The non-inferiority limit for missed diagnoses is 1%, i.e. the intervention will be deemed non-inferior if the difference between the allocated groups (intervention – control) is less than 1%. Therefore, the intervention will be deemed non-inferior if the upper limit of the 95% confidence interval lies below 1.

As for the primary endpoint, the analysis will be performed for all 17 study indications together. An analysis will be performed that only includes patients who have no indications in addition to the 17 study indications

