3.2. Randomisation

Participating PCPs were randomised to the intervention or to the control group. The unit of allocation is the PCP. This means that all physicians in the same practice were allocated to the same intervention and that either all or no physicians in the PCP were included in the trial. All patients cared for by the same primary care practice were exposed to the same intervention. We recruited 288 physicians on 01/12/2017 of which 8 physicians dropped out before including patients. The 280 physicians were distributed across 72 PCPs. We stratified the randomisation according to the laboratory with which they collaborated (3 strata). The level of confidence in using a CPOE was associated with the laboratory with which the PCP collaborated. This also assured that all PCPs collaborating with a laboratory were evenly distributed across both arms. Randomisation was done using a random numbers generator by the trial chief statistician. The research team will remain blinded to the allocation until after database lock. Further details on the randomisation scheme can be found in the protocol under 8.3.

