10.2. Analysis methods

10.2.1. Primary outcome analysis

Appropriateness

For the definition of the primary outcome, three numbers are relevant: (a) the number of requested tests which are appropriate, (b) the number of requested tests which are inappropriate and (c) the number of inappropriately not-requested tests. As indicated in section 5b, the latter number is only relevant for diabetes mellitus, chronic kidney disease, rheumatoid arthritis and thyroid disease. Per patient, aggregated over panels if multiple panels are available, the primary outcome is defined by the ratio $(a)/(a+b+c)$. We will refer to this ratio as the proportion of appropriate tests in the remainder.

To assess differences between the allocated groups in the proportion appropriate tests, a logistic generalized estimating equation (GEE) model will be used: of interest are the marginal proportions, not the proportions on patient, physician or PCP level.

The logistic GEE model will include the allocated group and laboratory as factors and PCP as the clustering variable. The effect of the intervention will be expressed as the difference in proportions and will be presented together with its associated 95% confidence interval. The proportion of appropriate tests in the two allocated groups will also be estimated from the GEE model and presented with their 95% confidence intervals.

Appropriateness for the composite of all study tests will be compared between intervention and control groups. Furthermore, an additional analysis will be performed that only includes patients who have no indications in addition to the 17 study indications. This additional analysis will correct for an overestimation of inappropriate tests when more than one indication is selected, including indications not under evaluation. These tests would be considered inappropriate even though they could be appropriate according to one of the other indications not being evaluated.

The analyses will be performed on all patients from all physicians according to their allocated group.

Appropriateness for each study indication separately will be performed as a secondary analysis. In this analysis we will include the number of additional indications for the panel as a factor in the analysis.

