10.2.2. Secondary outcome analysis

Diagnostic error

The proportion of patients with a missed diagnosis will be analysed by means of a logistic GEE model that includes allocated group and laboratory as factors and uses PCP as the clustering variable. An independent working correlation matrix will be used. The proportion of patients with a missed diagnosis and associated 95% confidence intervals will be estimated from the model.

The difference in proportions will be obtained by subtracting the two proportions. The associated standard error will be calculated from the rules for the variance of a difference between two independent estimates. The 95% confidence interval for the difference will be calculated.

The non-inferiority limit for missed diagnoses is 1%, i.e. the intervention will be deemed non-inferior if the difference between the allocated groups (intervention – control) is less than 1%. Therefore, the intervention will be deemed non-inferior if the upper limit of the 95% confidence interval lies below 1.

As for the primary endpoint, the analysis will be performed for all 17 study indications together. An additional analysis will be performed that only includes patients who have no indications in addition to the 17 study indications

Test volume

The total number of tests will be analysed using a GEE model for count data (Poisson or Negative Binomial to handle potential overdispersion) that includes allocated group and laboratory as factors in the model and PCP as clustering variable. No offset will be used. The number of tests per patient for each group will be estimated from the model and presented together with their associated 95%

confidence intervals. The effect of the intervention will be presented as the ratio between the two numbers with its 95% confidence interval. Statistical significance will be assessed at a significance level of 5%.

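### The interval that decides non-inferiority on missed diagnoses keeps a standard-error rule that no longer fits the SAP's model, and the laboratory weighting is not stated

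*SAP*

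**What the plan says.** Protocol 9.3.3.1 specifies a "logistic GEE model that includes a factor for allocated group and uses PCP as the clustering variable". SAP 10.2.2 changes the model to one that "includes allocated group and laboratory as factors and uses PCP as the clustering variable". Both documents then subtract one arm proportion from the other and use the same standard-error rule: "The associated standard error will be calculated from the rules for the variance of a difference between two independent estimates". Non-inferiority is declared when the upper end of the resulting 95% interval is under one percentage point.

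The SAP's only statement on how the arm proportions are formed is "The proportion of patients with a missed diagnosis and associated 95% confidence intervals will be estimated from the model". It gives no laboratory weights. For the primary outcome, SAP 10.2.1 does name a target: "of interest are the marginal proportions, not the proportions on patient, physician or PCP level". The diagnostic-error text has no equivalent. It refers back to the primary endpoint only to say that the 17 indications are analysed together.

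On allocation, SAP 3.2 states that "all physicians in the same practice were allocated to the same intervention", with randomisation stratified by laboratory.

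**The concern.** The model was updated and the variance formula was not. Under the protocol's model the two proportions come from disjoint sets of practices, so adding their variances is right. Under the SAP's additive model each proportion is built from the same estimated intercept and laboratory coefficients. The variance of the difference is then Var(p1) + Var(p0) − 2Cov(p1, p0), and the rule omits the last term.

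The sign and size of that term depend on how laboratories are weighted, which is left open. The weighting can also move the estimate: averaging laboratories equally on the logit scale does not give the marginal proportions to which an absolute 1% margin naturally refers.

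The upper limit of this interval is the non-inferiority decision. SAP section 8 unblinds the study team at database lock, before the analysis, so a weighting not fixed by then could be chosen with results in view.

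**Working it through.** **Planning figures.** For 2.5% in both arms, margin 1%, one-sided 5% and 80% power, n per arm = (1.645 + 0.842)² × 2 × 0.025 × 0.975 / 0.01² ≈ 3014, or 6028 in total, against 6032 in Protocol 9.1.2. The SAP 3.3 requirement also reproduces: 6032 × [1 + 0.025 × (45.5 − 1)] = 12743, against 12740.

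**Expected precision.**
- Inputs: 280 physicians in 72 practices (SAP 3.2), 11200 patients (SAP 3.3), about 15% without an eForm (SAP 10.3), rate 2.5% and ICC 0.025 (Protocol 9.1.2).
- Patients analysed: 11200 × 0.85 = 9520, or 34 per physician. Design effect: 1 + 0.025 × 33 = 1.825.
- SE = √(2 × 0.025 × 0.975 × 1.825 / 4760) = 0.00432.
- With no true difference, the expected upper limit is 1.96 × 0.432 = 0.85 points, against a limit of 1.00.
- Power = Φ(0.01/0.00432 − 1.96) = 63.8%. If the interval uses an SE 2% too large, it is Φ(0.01/0.00432 − 1.02 × 1.96) = 62.3%.

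**Linear check of the covariance.** Let w be the laboratory weights, n the laboratory sizes, n₁ and n₀ the arm sizes within each laboratory, and π the weighted intervention share. Then Cov/σ² = Σ(w²/n) − π(1−π)/Σ(n₁n₀/n). Enrolled practices per laboratory are not given, so a 1:1:2 split is assumed from Protocol section 4: "Both MCH and Anacura provide laboratory services to around 500 primary care physicians, whereas AML delivers services to about 1000 physicians". With sizes 1, 1 and 2, arms balanced within laboratories and weights of 1/3:
- Σ(w²/n) = (1/9)(1 + 1 + 0.5) = 0.278, and the second term is 0.25/1 = 0.25.
- Covariance = 0.278 − 0.25 = 0.028. Each arm variance = 0.278 + 0.25 = 0.528.
- Correlation = 0.028/0.528 = 0.053. SE ratio (rule/correct) = √[1/(1 − 0.053)] = 1.027.

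If the weights equal the observed mix and arms are balanced within laboratories, the covariance is zero. If arm shares differ between laboratories it becomes negative, and the rule is then too narrow.

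**Simulation.** 6000 trials per scenario, true difference 0, 9520 patients, physician-level ICC 0.025, randomisation stratified by laboratory, logistic GEE with independence working correlation and practice-robust covariance. Practice splits and laboratory rates are assumptions. Equal laboratory weights on the logit scale:

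| Practices per laboratory; laboratory rates | SE ratio, median (2.5–97.5%) | Verdict changes |
|---|---|---|
| 24/24/24; all 2.5% | 1.00 (0.96–1.05) | 1.1% |
| 18/18/36; all 2.5% | 1.02 (0.96–1.13) | 2.3% |
| 18/18/36; all 2.5%; uneven recruitment per physician | 1.02 (0.94–1.14) | 3.1% |
| 18/18/36; 1.5/2.5/3.0% | 1.08 (0.97–1.28) | 4.8% |
| 18/18/36; 3.5/2.5/2.0% | 1.005 (0.96–1.09) | 1.9% |

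The group-only model gives a ratio of 1.000 in every trial. Weighting by the observed mix gives a median of 0.998 (0.96–1.03), with 0.5–0.8% of verdicts changed. In the 18/18/36 equal-rate case the rule was too wide in 72% of trials and too narrow in 28%. It lost 1.9% of verdicts and gained 0.4%, so non-inferiority was shown in 63.7% of trials instead of 65.2%.

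A second simulation, with 11200 patients and recruitment per physician varying (coefficient of variation 0.8), gives 1.015 for 18/18/36 with equal weights and 0.999 with the observed mix. If arms are deliberately unbalanced within laboratories, the observed-mix ratio is 0.989 (0.93–1.05). Its most skewed case (10/12/50, equal weights, rates 1.5/2.5/3.5%) reaches 1.25.

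**Estimate.** With laboratory shares 0.25/0.25/0.50 and a common odds ratio set so that the marginal difference is exactly 1.00 point, equal-weight logit means show 1.00 point (equal laboratory rates), 0.90 (1.5/2.5/3.0%) or 1.04 (3.5/2.5/2.0%).

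**The case against.** The covariance is close to zero under the reading the SAP most naturally suggests. SAP 10.2.1 speaks of marginal proportions, which points to the observed mix, and stratification by laboratory keeps the arms balanced. One further run under that reading gave a ratio of 1.000 (0.991–1.008) and 0.1% of verdicts changed. The larger figures need equal weights, which no section specifies, together with splits and laboratory rates that the documents do not give.

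The error is also mostly conservative. At a true excess of one point, false non-inferiority in the 18/18/36 case with the observed mix is 3.4% with either SE. With 10/12/50 and equal weights it is 2.4% under the rule and 3.6% with the covariance kept, against a nominal 2.5%. Finally, the share of changed verdicts is near its peak at a 2.5% rate. Protocol 9.1.2 cites 2–3 incidents per hundred, of which 4–45% are diagnostic, implying 0.08–1.35%. At 1.35% the equal-weight share falls from 2.1% to 1.5%.

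All of this stands as a limit on size. It does not make the rule right for the stated model. The reassuring figures also assume an observed-mix weighting that the diagnostic-error text never states.

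**Conclusion.** The concern holds. The SAP's standard-error rule belongs to the protocol's group-only model and is not correct for the group-plus-laboratory model, and nothing elsewhere fixes the weighting or restores the covariance. The effect is small: essentially none at the median under observed-mix weighting, and about 0–8% too wide at the median under equal weights in the tabulated scenarios, with errors in either direction in single trials. False non-inferiority is not materially inflated. The equal-weight sizes rest on assumed laboratory splits and rates; the omission itself rests on no assumption. It is worth correcting because the interval is the decision and its expected upper limit, 0.85 against 1.00, leaves little room.

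**What to change.** In SAP 10.2.2, replace the standard-error sentence with: *The arm proportions are standardised over the observed laboratory distribution, and the standard error of their difference is obtained by the delta method from the full PCP-robust covariance matrix of the GEE, including the covariance between arms.* For a group-only model this reduces to the protocol's rule.

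The cost is one sentence and a few lines of SAS code, with no extra data, and it should be settled before database lock. One reservation: with 72 practices the robust standard error is itself slightly small (3.4% one-sided error against 2.5%), and this change does not correct that. Whether to add a small-sample correction is a separate decision. The same method can serve the primary outcome's difference. SAP 10.2.1 states no standard-error rule there, so no error is claimed for it.

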## 8.6 Baseline data

Baseline data to compare participating physicians will be obtained at the start of the study. This data includes:

- Size of the PCP (how many active physicians)
- Age of the participating physician at the start of the study
- Sex of the participating physician
- Number of active years in general practice of the participating physician at the start of the study
- Average number of tests per laboratory order in the three months prior to the study, as a measure of baseline testing volume
- Experience in the use of a CPOE prior to the study

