# 9 STATISTICS AND DATA ANALYSIS

## 9.1 Sample size calculation

Our study involves multiple levels which are not independent of each other. Lowest on the level of analysis is the individual laboratory test included in our study. We must account for the fact that these tests are not ordered entirely independent of each other in one patient, for instance, a white blood cell count is often ordered together with a white blood cell differentiation. In our analysis we will account for this level of clustering. Additionally, there is clustering on the level of the physician. When the same physician orders tests for various patients over time, each of these orders is not independent of the other. For instance, if a physician often requests chloride in patients taking diuretics, then this will probably be so in all patients taking diuretics. We must therefore also account for clustering on the level of the physician. Finally, GP's often work in primary care practices. Physicians working in the same practice tend to have similar ordering behaviour implying that the orders made by two physicians in the same practice are not independent of each other. This is the last level of clustering for which we will account. We therefore have a 4 level setting comprising test, patient, physician and primary care practice:

1. Multiple study tests per patient, assumed to be 5 per patient,
2. Multiple patients per physicians, assumed to be 42 per 3 months if there is 70% use of the online intervention,
3. Multiple physicians per primary care practice (PCP), assumed to be 2.35 based on preliminary data by Heselmans et al ([Heselmans 2013](#)).

Each of these clustering levels inflates the required sample size.

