## 9.5 Adjusted analysis

For the primary endpoint and the missed diagnoses, the following adjusted analyses will be performed:

- Volume of physician practice, i.e. the total number of tests prescribed the previous year.
- Total number of patients in practice
- Physician's age or years worked.

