3.3. Sample size

For sample size calculations, we refer to the protocol and appendix 3 of the protocol. At the end of the six-month intervention period the planned sample size was verified based on the number of recruited physicians and the average number of patients per physician. With 280 study physicians (clusters), a sample of 12740 patients (45.5 patients on average per physician) would be necessary to have at least 80% power for the secondary outcome (diagnostic error), assuming the original intra-cluster correlation and diagnostic error rates. At that point we had recruited 11200 patients and it was deemed unfeasible to recruit an additional 1500 patients. Since most recruitments were realised by physicians who had already recruited 50 or more patients, the Steering Committee agreed that attempts to recruit additional patients should target physicians with a low number of recruited patients. Therefore, only those physicians who had not yet recruited 10 patients were allowed another month to recruit additional patients. Specific calculations regarding the sample size and the assumed intra-cluster correlations can be found in the protocol under 9.1.

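### The SAP's test-volume model omits the baseline testing volume that the protocol plans to obtain, and so gives up some precision on a secondary outcome

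*SAP*

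**What the plan says.** SAP 10.2.2 (Test volume) specifies a Poisson or negative binomial GEE model that "includes allocated group and laboratory as factors in the model and PCP as clustering variable. No offset will be used". The result is a ratio of tests per patient with a 95% confidence interval, tested at 5%. SAP 2.2.3 hypothesises a 20% reduction. The protocol's version (9.3.3.2) had allocated group as its only factor and physician as the cluster. The SAP therefore added the stratification factor and moved the cluster to the randomised unit, but it added no baseline term.

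Protocol 8.6 lists among the baseline data "Average number of tests per laboratory order in the three months prior to the study, as a measure of baseline testing volume". The use it states for these data is to compare participating physicians. Protocol 9.5 does use a prior-volume measure for adjustment. It opens with "For the primary endpoint and the missed diagnoses, the following adjusted analyses will be performed", and its first item is "Volume of physician practice, i.e. the total number of tests prescribed the previous year". Test volume is not among the outcomes it covers. The SAP has no adjusted-analysis section.

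**The concern.** A physician's earlier ordering is the natural predictor of later ordering. Prior volume is used for two outcomes it may predict only loosely, and not for the one it should predict best.

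Precision on this outcome depends mainly on the number of practices. Randomisation is by primary care practice (PCP), and Protocol 9.1 states that "Physicians working in the same practice tend to have similar ordering behaviour". Protocol 4 expected about 124 PCPs, but the trial has 72. For the between-PCP component alone, that raises the standard error by a factor of sqrt(124/72) = 1.31. Laboratory is the only stratum (SAP 3.2), so baseline volume is neither balanced by design nor adjusted for. What is at stake is the width of the interval for the volume ratio and, if PCPs differ widely, some power.

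**Working it through.** **No stated figure to reproduce.** The documents give no sample size, power, CV, ICC or baseline correlation for test volume.

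**Inputs from the documents**
- Clusters: "The 280 physicians were distributed across 72 PCPs" (SAP 3.2). Equal arms of 36 PCPs are assumed.
- Patients: "At that point we had recruited 11200 patients" (SAP 3.3), so 11200/72 = 155.6 per PCP.
- Effect: ratio 0.80, |ln 0.80| = 0.2231. The 5% level is taken as two-sided.

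**Assumed inputs**
- r, the PCP-level correlation of baseline with follow-up volume: 0.3, 0.5, 0.7.
- CVb, between PCPs: 0.2 and 0.3.
- CVw, between patients within a PCP: 0.6.

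**Does laboratory already do this job?** Protocol 4 states: "On average physicians order 14.61 tests per panel at AML, 14.2 tests at Anacura and 14.25 tests at MCH". The mean is 14.35 and the SD 0.183, so the CV is 0.0127. The share of between-PCP variance explained is 0.0127²/0.2² = 0.40%, or 0.18% at CVb 0.3. It does not.

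**Precision.** Var(log ratio) = 2 × [CVb²(1 − r²)/36 + CVw²/(36 × 155.6)], and power = Φ(0.2231/SE − 1.96).

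At CVb 0.2 without the covariate: 2 × [0.04/36 + 0.36/5600] = 2 × [0.001111 + 0.000064] = 0.002351, so SE = 0.0485. About 94.5% of this variance lies between PCPs, which is the part a physician or PCP baseline can explain.

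| CVb | r | SE | CI narrowing | Power |
|---|---|---|---|---|
| 0.2 | none | 0.0485 | – | 99.6% |
| 0.2 | 0.3 | 0.0464 | 4.3% | 99.8% |
| 0.2 | 0.5 | 0.0424 | 12.6% | >99.9% |
| 0.2 | 0.7 | 0.0355 | 26.7% | >99.9% |
| 0.3 | none | 0.0716 | – | 87.6% |
| 0.3 | 0.3 | 0.0684 | 4.5% | 90.4% |
| 0.3 | 0.5 | 0.0623 | 13.0% | 94.8% |
| 0.3 | 0.7 | 0.0518 | 27.7% | 99.1% |

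With CVw raised to 1.0 at CVb 0.2, the narrowing is 4.0%, 11.4% and 24.0%, so the result depends little on that input.

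**How wide can CVb plausibly be?** The implied ICC is CVb²/(CVb² + CVw²): 0.04/0.40 = 0.10 at CVb 0.2, 0.09/0.45 = 0.20 at 0.3, and 0.16/0.52 = 0.31 at 0.4. Protocol 9.1.1 cites 0.04 to 0.288 for appropriateness of laboratory tests and calls its own choice of 0.2 very conservative. It cites nothing for volume. CVb 0.4 is therefore only an extreme case: SE 0.0950, power 65.2% unadjusted, and 69.2%, 77.2% and 90.5% at r = 0.3, 0.5 and 0.7.

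**Second parametrisation.** With total patient CV 0.4, 0.6 or 0.8 and ICC 0.05, 0.1 or 0.2, unadjusted power is at least 93.6% in eight of nine settings. In the ninth (CV 0.8, ICC 0.2) it is 74%, rising to 78%, 85% and 95% at r = 0.3, 0.5 and 0.7.

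**Simulation check.** A Poisson GEE with independence working correlation was fitted to simulated data with 72 PCPs of unequal size (average about 60 patients), three laboratories and CVb 0.2, with 400 runs per value of r. The SE fell by 4%, 14% and 27% at r = 0.3, 0.5 and 0.7. The mean log ratio was about −0.22 with and without the covariate. At r = 0 nothing was lost (0.0620 against 0.0621).

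**The case against.** A model with arm, the stratification factor and the randomised unit as cluster is sound, and the SAP's version already improves on the protocol's. Nothing in the documents is contradicted. That stands, and it limits the point to an improvement.

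The size rests wholly on assumed inputs. That also stands. The correlation may be low: Protocol 4 says only about 30% of physicians used the electronic order system beforehand, and the baseline is per order while the result is reported per patient.

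The change may not be cheap. Protocol 8.6 states an intention and names no source. The laboratory deliveries in Protocol 8.7 (Month 12) and 8.8 (Month 24) list no pre-study volume, and SAP 6.1 lists no table that holds it. SAP 6.4.1 replaces the physician identifier, and SAP 7.2 locks the laboratory database before the final data collection. A physician-specific continuous value may also need a fresh small-cell review. These obstacles are real, so the fix is conditional on the data.

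A reader might infer that the trial is underpowered for volume, or that adjustment would add 25 points of power. That gain (65.2% to 90.5%) needs both CVb 0.4 and r = 0.7, and CVb 0.4 implies an ICC above the range the protocol cites. A reader might also infer bias from the omission. Randomisation protects the unadjusted ratio, and the simulation shows the same estimate either way.

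Which tests and records the volume outcome counts is a separate question (Protocol 3.3.2.2 and SAP 2.2.3 against Protocol 8.1.1, Protocol 9.7 and SAP 7.1). It should be handled as its own point, noting that Protocol 8.7 already schedules paper-order counts and volumes. Its answer could change the cluster size used above and the best form of the covariate.

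**Conclusion.** The omission is real and worth correcting if the baseline values are available. It is a missed precision gain on one secondary outcome; the planned analysis remains valid. The dependable benefit is a narrower interval, by about 4% to 27% for r between 0.3 and 0.7. A useful power gain arises only if PCPs differ widely in volume, and the documents do not say whether they do. The result assumes 36 equal-sized PCPs per arm and the CVs and correlations listed above. Confidence in the omission is high. Confidence in the size of the gain is limited, because none of the variance inputs comes from the documents.

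**What to change.** 1. Confirm that the Protocol 8.6 baseline values were obtained for the 280 physicians and can be linked to the analysis data. If not, the planned model stands unchanged.
2. If they exist, issue a dated and signed SAP amendment before the laboratory database is locked and physician identifiers are recoded. Waiting only for unblinding would be too late. The chief statistician performed the randomisation and holds the scheme (SAP 3.2 and 8), so the amendment should record that the allocation was not used.
3. Add log baseline tests per order (physician value or PCP mean) to the volume GEE model. Keep laboratory as a factor and PCP as the cluster.
4. State how group means are standardised over the covariate, and give a rule for missing baseline values.
5. Report the unadjusted ratio as a sensitivity result.

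The cost is one model term and a short amendment, plus retrieving and linking the baseline values, and possibly a small-cell check. No new patient data are needed.
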